#### 2. STUDY OBJECTIVES AND ENDPOINTS

#### 2.1. Study Objectives

The overall study objectives are to evaluate the efficacy and safety of zetomipzomib in patients with active Class III or IV (with or without Class V; Class III/IV +/-V) LN and for those with pure Class V LN. The primary, secondary, and exploratory objectives and endpoints are summarized below.

The primary and secondary efficacy objectives are to evaluate zetomipzomib compared with placebo in patients with active Class III/IV +/-V LN on background MMF or equivalent, and corticosteroids based upon current guideline-driven standard of care. Patients with pure Class V LN on similar background therapy will also be evaluated as a subgroup.

The primary safety objective is to determine the safety and tolerability of zetomipzomib in patients with active LN on background standard of care, MMF or equivalent, and corticosteroids.

The exploratory objectives include the following, each on background standard of care:

- To evaluate the speed of action of zetomipzomib compared with placebo
- To evaluate the clinical benefit of zetomipzomib compared with placebo
- To evaluate changes in serum levels of selected parameters in zetomipzomib compared with placebo
- To evaluate the efficacy of zetomipzomib compared with placebo on clinical lupus disease assessments
- To evaluate the efficacy of zetomipzomib compared with placebo on improving patient's quality of life
- To evaluate relapse in zetomipzomib compared with placebo
- To evaluate glucocorticoid-related AEs in zetomipzomib compared with placebo
- To evaluate renal histopathology and immunohistopathology (at selected sites based on feasibility)
- To evaluate biomarkers
- To evaluate the pharmacokinetics of zetomipzomib

# 2.2. Study Endpoints

#### 2.2.1. Definitions Related to Efficacy Endpoints

Baseline values for 24-hour UPCR and all other endpoints are defined in Section 10.6.

#### CRR:

• A UPCR ≤0.5 in one 24-hour urine sample (for Weeks 13, 25, 37 [primary endpoint], and 53) or 2 consecutive first morning void urine samples (for all other time points).

- An eGFR ≥60 mL/min/1.73 m^2 or no confirmed decrease of >20% from Baseline eGFR.
- Partial renal response (PRR):
- A  $\geq$ 50% reduction of UPCR from Baseline, and to <1.0 if the Baseline UPCR was <3.0 or to <3.0 if the Baseline value was  $\geq$ 3.0.

#### Responder requirements:

- Should not have received more than 10 mg prednisone or equivalent for ≥3 consecutive days or for ≥7 days in total during the 8 weeks prior to a CRR assessment.
- No use of rescue medication (see Section 6.2.3) or concomitant medication, except those required or permitted (see Sections 6.2.1 and 6.2.2, respectively) sufficient to be a treatment failure (see Section 2.2.5) as determined by the Clinical Endpoints Committee (CEC, see Section 9.10).
- Patient has data available for endpoint assessment.

Relapse: loss of CRR at 2 consecutive time points

Proteinuric flare: doubling from lowest UPCR and (if CRR then >1 or if PRR then >2) at 2 consecutive time points

Time to death or renal-related events: defined as the first occurrence among the following:

- 1. Death
- 2. Doubling of serum creatinine
- 3. Proteinuric flare
- 4. Renal event-related treatment failure

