#### 2.2.3. Exploratory Endpoints

The exploratory endpoints for patients treated with zetomipzomib compared with placebo include the following:

- Proportion of patients achieving PRR with successful taper of prednisone or equivalent to ≤5 mg by Week 17
- Proportion of patients achieving PRR with no use of prednisone or equivalent during the 8 weeks prior to the renal response assessment
- Proportion of patients who develop doubling of Baseline serum creatinine, kidney failure (receiving dialysis or kidney transplantation), or death
- Change from Baseline in antibodies (anti-dsDNA antibody, C1q autoantibody) and time to antibodies normalization or negative status (anti-dsDNA antibody normalization, anti-C1q antibody negative status)
- Change from Baseline in complement (C3, C4) and time to complement (C3, C4) normalization status
- Change from Baseline in 24-hour urine protein
- Change from Baseline in serum albumin
- Change from Baseline in serum creatinine
- Change from Baseline in eGFR

- Change from Baseline in serum lipids (serum low-density lipoprotein [LDL] cholesterol, serum total cholesterol, serum triglycerides)
- Change from Baseline in blood hemoglobin A1c (HbA1c)
- Change from baseline in the Glucocorticoid Toxicity Index (GTI) as measured by the Cumulative Worsening Score (GTI-CWS) and the Aggregate Improvement Score (GTI-AIS)
- Proportion of patients with Baseline SLEDAI-2K, excluding renal components, ≥6 with at least a 4-point improvement
- Change from Baseline in SLEDAI-2K
- Change from Baseline in 28-joint counts
- Change from Baseline in physician global assessment of disease activity (PGA) score
- Proportion of patients with relapse or proteinuric flare
- Time to relapse or proteinuric flare
- Proportion of patients with SLE Flare Index of severe, moderate, or mild
- Time to SLE Flare Index of severe, moderate, or mild
- Change from Baseline in renal biopsy histopathology and immunohistopathology (optional)
- Pharmacogenomics profile (ribonucleic acid [RNA] sequencing) and biomarkers, such as serum cytokine levels and circulating leukocytes to be determined in blood samples and urinary biomarkers
- Pharmacokinetics profile

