## 7. STUDY EVALUATIONS

## 7.1. Schedule of Assessments

Efficacy and safety assessments will be performed, and zetomipzomib or placebo will be administered according to the Schedule of Assessments (Appendix 3). A safety follow-up visit will occur 4 weeks after the last dose of zetomipzomib or placebo (EOS visit). In addition, monthly visits at Weeks 1, 5, 9, 13, 17, 21, 25, 29, 33, 37, 41, 45, 49, and 53, as well as the EOS visit (Week 56) and the ETV, must all be performed at the investigational site. All other study visits may occur either at the investigational site or the patient's location.

The first and second doses of zetomipzomib or placebo must be administered at the investigational site on Day 1 (Week 1) and Week 2. Following Week 2, zetomipzomib or placebo injections will either be self-administered by the patient/caregiver or via home health service at patient's location, as appropriate, or by study personnel at the investigational site.

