# APPENDIX 3. SCHEDULE OF ASSESSMENTS

Site Visit Week	Sc	1	2	5	9	13	17	21	25	29	33	37	41	45	49	53 EOT	56 EOS a	ETV
Assessment Window (days)	-35 to -1	NA	±2	±2	±2	±2	±2	±2	±2	±2	±2	±2	±2	±2	±2	±2	±2	NA
Informed consent	X																	
Medical history, including prior medications	X																	
Infectious disease blood tests b	X																	
Serum pregnancy test	X																	
Hepatitis B DNA c		X				X			X			X				X	X	X
Chest x-ray d	X																	
EULAR/ACR criteria for SLE	X																	
Physical examination e	X	X	Х	X	X	X	X	X	X	X	X	X	X	X	X	X	X	X
12-lead ECG with QTcF interval f	X								X							X		X
Vital signs g	X	X	X	X	X	X	X	X	X	X	X	X	X	X	X	X	X	X
Clinical lupus disease assessmentsh	X	X				X			X			X				X	X	X
EQ-5D-5L		X				X			X			X				X	X	X
GTI assessment (including labs i )		X							X							X		X
Estimated GFR	X	X		X	X	X	X	X	X	X	X	X	X	X	X	X	X	X
Clinical laboratory tests j	X	X		X	X	X	X	X	X	X	X	X	X	X	X	X	X	X
Anti-dsDNA and complements (C3 and C4)	X	X		X	X	X	X	X	X	X	X	X	X	X	X	X	X	X
C1q autoantibody and quantitative IgM, IgG, IgA		х				X			X			X				X	X	X
Urine pregnancy test k		X		X	X	X	X	X	X	X	X	X	X	X	X	X	X	X
24-hour urine test	X					X			X			X				X	X	X
First morning void urine test	X			X	X	X	X	X	X	X	X	X	X	X	X	X	X	X
IV methylprednisolone 		X																
Background medications 	←																	

Site Visit Week	Sc	1	2	5	9	13	17	21	25	29	33	37	41	45	49	53 EOT	56 EOS a	ETV
Zetomipzomib or placebo administration m			← zet	omipz	omib	or pla	cebo a	admin	istrati	on fro	m Wee	k 1 to	Week	52 →				
Renal histopathology and immunohistopathology n	X															X		X
Urine biomarker measurements	X					X			X			X				X	X	X
Blood biomarker measurements o		X				X			X			X				X	X	X
Sparse PK assessment p									X			X						
Optional PK assessment p				X														
AEs and concomitant medications q	← AEs and concomitant medications collected from Week 1 to Week 52, Week 53, Week 56, and ETV →																	

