3.2.1.3. Time-to-event endpoints

When calculating the time-to-CRR or time-to-PRR endpoints, all timepoints where UPCR data is collected will be considered. The UPCR criteria for CRR/PRR may be met using the 24-hour urine tests for Weeks 13, 25, 37, and 53. For all other timepoints, UPCR criteria for CRR/PRR will use 2 consecutive first morning void (FMV) urine tests.

When calculating time-to-FMV-CRR and time-to-FMV-PRR endpoints, if the 24-hour urine test is not available, then 2 consecutive FMV urine tests may be used at Weeks 13, 25, 37, and 53. For all other timepoints, UPCR criteria for CRR/PRR will use FMV urine tests.

Any time the 24-hour urine test is available and valid it should be used for analysis over the FMV urine test (Weeks 13, 25, 37, and 53).

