3.2.1.4. Treatment Failure

A patient experiencing one or more of the following criteria define treatment failure:

- Prednisone or equivalent* beyond that permitted (see Section 6.2.1.2 of the study protocol), to include:
 - >10 mg/day for ≥3 consecutive days or for ≥7 days in total during the 8 weeks prior to the renal assessment at
- MMF or equivalent* >2 g/day after Week 25
- Requiring rescue therapy (see Section 6.2.3 of the study protocol for details), as verified by the CEC

Statistical Analysis Plan, Version 1.0 Date Issued: 24Jul2024

• Use of prohibited medications (see Section 6.2.4 and Appendix 2 of the study protocol for details) or inappropriate use of the required concomitant medications (see Section 2.2.5 of the study protocol), as determined through manual data review by the CEC

• Discontinuation of zetomipzomib or placebo

Whenever possible, a complete disease activity assessment (eg, SLEDAI-2K, SLE flare index, PGA) and laboratory assessments (hematology, chemistry, urinalysis, anti-dsDNA, and C3 and C4) should be performed to document flare prior to initiating treatment that results in a treatment failure designation. Treatment failure does not necessarily require discontinuation of zetomipzomib or placebo. See Section 8.1.2 of the study protocol for individual patient stopping rules.

Treatment failure will be adjudicated in blinded fashion by the CEC. Details of this process will be provided in the separate CEC Charter.

*See Appendix 2 for dose conversion of other corticosteroid medications to prednisone equivalent and conversion of mycophenolic acid (MPA) and mycophenolate sodium (MPS) to MMF equivalent.

3.2.1.5. **Relapse**

Relapse is defined as loss of CRR at 2 consecutive time points

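### Because adjacent visits share a first-morning-void sample, one high spot sample can meet the two-time-point definition of relapse

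*Protocol*

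**What the plan says.** Protocol 2.2.1 gives relapse one line: "Relapse: loss of CRR at 2 consecutive time points". SAP 3.2.1.5 repeats it: "Relapse is defined as loss of CRR at 2 consecutive time points". Neither says what losing CRR means at the level of a urine sample.

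For CRR, Protocol 2.2.1 uses one 24-hour collection at Weeks 13, 25, 37 and 53, and otherwise "2 consecutive first morning void urine samples (for all other time points"). Protocol 7.1 lists "monthly visits at Weeks 1, 5, 9, 13, 17, 21, 25, 29, 33, 37, 41, 45, 49, and 53", so site visits from Week 5 are four weeks apart. In Appendix 3 the row "First morning void urine test" shows one test at each of those visits. Two consecutive FMV samples therefore come from two adjacent visits.

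The SAP is less clear. Its CRR definition (3.2.1.1) names only the four 24-hour weeks. The two-sample rule appears in 3.2.1.3: "For all other timepoints, UPCR criteria for CRR/PRR will use 2 consecutive first morning void (FMV) urine tests". That sentence sits in a paragraph about time to CRR and time to PRR, and relapse is not mentioned there.

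Relapse feeds two exploratory endpoints: "Proportion of patients with relapse or proteinuric flare" (Protocol 2.2.3, SAP 8.5.3) and the matching time-to-event endpoint (SAP 8.5.2).

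**The concern.** Asking for two time points normally serves to confirm: one stray spot UPCR should not end a remission. If the status at each of two adjacent visits depends on the same sample, that safeguard is missing, because one measurement is counted twice. A patient whose other samples, including the neighbouring 24-hour collections, are all at or below 0.5 could be recorded as relapsed.

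Evaluating relapse is a stated exploratory objective. Only patients who have reached CRR can relapse, so spurious relapses arise in proportion to the responders in each arm. Different programmers could also read the definition differently and obtain materially different counts.

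**Working it through.** The documents give no relapse rate, so there is no figure to reproduce. The check has two parts.

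**1. Which single samples trigger a relapse.** Inputs: the visit grid (Protocol 7.1), one FMV per visit (Appendix 3), the Protocol CRR rule, and 'loss' read as 'CRR definition not met'. Take a patient in CRR at Week 25, with one FMV above 0.5 and every other sample at or below 0.5. The documents do not say whether a visit's pair is its own sample plus the previous one or plus the next one, so both are shown.

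| High FMV at week | CRR unmet, current + previous | Relapse? | CRR unmet, current + next | Relapse? |
|---|---|---|---|---|
| 29 | 29, 33 | yes | 29 | no |
| 33 | 33 | no | 29, 33 | yes |
| 41 | 41, 45 | yes | 41 | no |
| 45 | 45, 49 | yes | 41, 45 | yes |
| 49 | 49 | no | 45, 49 | yes |

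Either way, 3 of 5 positions trigger. In the other two the adjacent visit (Week 25, 37 or 53) is assessed on a 24-hour sample, so the run stops at one. Starting from CRR at Week 13 adds Weeks 17 and 21, of which one triggers (17 or 21, depending on pairing), giving 4 of 7. Extending to Week 56 adds none.

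**2. How often this could happen without a true relapse.** Let *p* be the chance that one FMV exceeds 0.5 in a patient still in remission, independent between samples, with the 24-hour samples always at or below 0.5. Using current-and-previous pairs from Week 25:

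- Block of Weeks 29 and 33: relapse if FMV 29 is high, or if FMVs 25 and 33 are both high: a = p + (1−p)p².
- Block of Weeks 41, 45 and 49: relapse if FMV 41 or 45 is high; if both are low, CRR is met at Week 45 and the run is broken: b = 1 − (1−p)².
- Literal rule: 1 − (1−a)(1−b).
- Two separate samples required: a′ = p², b′ = p[1 − (1−p)²], total 1 − (1−a′)(1−b′).

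At p = 10%: a = 0.109 and b = 0.19, so the literal rule gives 1 − 0.891 × 0.81 = 27.8%. With separate samples, a′ = 0.01 and b′ = 0.019, giving 1 − 0.99 × 0.981 = 2.9%. At p = 5% the pair is 14.5% and 0.7%; at p = 20% it is 50.8% and 10.9%. Starting from Week 13, with a second two-visit block, the literal rule gives 19.0%, 35.7% and 62.3% for p = 5%, 10% and 20%, against 1.0%, 3.9% and 14.5%.

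Allowing noise in the 24-hour samples too, with lognormal UPCR, p = 1 − Φ(ln(0.5/median)/SD), and the 24-hour log-SD taken as 0.7 times the FMV log-SD, from Week 25:

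| Assumed median UPCR | Assumed FMV log-SD | p | Literal rule | Two separate samples |
|---|---|---|---|---|
| 0.25 | 0.3 | 1.0% | 3% | <0.1% |
| 0.30 | 0.4 | 10.1% | 29% | 4% |
| 0.35 | 0.5 | 23.8% | 62% | 22% |

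Both pairings give the same rates.

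**The case against.** The strongest reply is that the overlap depends on one reading of an unfinished definition. If relapse uses the SAP's own CRR definition (3.2.1.1), its time points are 24-hour collections and share no sample. If losing CRR means that the visit's own UPCR is above 0.5, two high samples are already needed. This stands in part: the documents do not adopt the problematic reading expressly. They do not exclude it either, and it is what the Protocol's wording yields. The 24-hour-only reading has its own difficulty: consecutive time points are then 12 to 16 weeks apart, and a patient first in CRR at Week 37 has only Week 53 left and so could never be classed as relapsed.

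The second reply is that little hangs on it. These endpoints are exploratory and outside type I error control. CRR and PRR at Weeks 25, 37 and 53 rest on 24-hour samples, and proteinuric flare is defined on UPCR values. All of that stands.

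A reader might infer three stronger things that the documents do not support:

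- *Any high spot sample counts as a relapse.* The table shows that two of the five positions do not trigger one.
- *The relapse endpoints would mostly count noise.* The documents give neither a within-patient variance nor a true relapse or flare rate, so the share of spurious events cannot be stated.
- *The drug would be made to look less durable.* An arm with more responders has more patients at risk of relapse under any definition; the overlap adds to that. For illustration, take 40% and 20% responders (the planning rates, applied here to Week 25) and no true relapse. The middle scenario gives 0.29 × 40% = 11.6% against 0.29 × 20% = 5.8% of randomized patients, compared with 1.6% and 0.8% when separate samples are required. This shows a direction under assumptions, not an established bias.

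**Conclusion.** The point holds in limited form. Under the Protocol's CRR rule and sampling schedule, one FMV above 0.5 can satisfy the relapse definition at 3 of the 5 FMV-assessed visits after Week 25, and the SAP does not settle which CRR rule applies. That part is deterministic; it rests only on reading loss of CRR as the definition not being met.

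The range of 3% to 62% against under 0.1% to 22% is illustrative. It rests on assumed medians, assumed log-SDs and independence between visits. Positive correlation between visits would raise the two-sample rate and narrow the gap. The consequence is confined to the proportion with, and the time to, relapse or proteinuric flare. The primary and key secondary endpoints and the definition of proteinuric flare are untouched.

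**What to change.** In Protocol 2.2.1 and SAP 3.2.1.5, define relapse after a first CRR as UPCR above 0.5, or failure of the eGFR condition, on the separate samples of two consecutive visits. Use the 24-hour sample at Weeks 13, 25, 37 and 53 and that visit's single FMV elsewhere. No lone high sample can then count.

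A definition on UPCR and eGFR alone would drop patients who lose response through the responder requirements, for example after rescue that brings UPCR back down. The same text should therefore state explicitly how treatment failure adjudicated by the Clinical Endpoint Committee after CRR counts towards relapse.

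Cost: a change of definition in both documents and the matching programming. No new data are needed, and fewer relapses will be counted. It should be settled before unblinding.

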#### 2.2.2. Efficacy Endpoints

#### 2.2.2.1. Primary Efficacy Endpoint

The primary efficacy endpoint is the proportion of patients achieving CRR at Week 37.

CRR will be adjudicated by the CEC (Section 9.10). The estimand description is provided in Section 10.6.1.1.

#### 2.2.2.2. Key Secondary Efficacy Endpoints

The key secondary efficacy endpoints will evaluate the proportion of patients achieving the following:

- PRR at Week 37
- CRR at Week 53
- PRR at Week 53
- CRR at Week 25
- PRR at Week 25

#### 2.2.2.3. Other Secondary Endpoints

The other secondary efficacy endpoints include the following:

- Percentage change from Baseline in UPCR by visit
- Time to CRR
- Time to PRR
- Time to death or renal-related events
- Proportion of patients achieving CRR (at Weeks 25, 37, and 53) with successful taper of prednisone or equivalent to <5 mg by Week 17
- Proportion of patients achieving CRR (at Weeks 25, 37, and 53) with no use of prednisone or equivalent during the 8 weeks prior to the renal response assessment
- Proportion of patients with UPCR ≤0.5 at Weeks 13, 25, 37, and 53
- Proportion of patients achieving CRR with UPCR ≤ upper limit of normal (ULN) at Weeks 25, 37, and 53
- Change from Baseline in clinical Systemic Lupus Erythematosus Disease Activity Index 2000 (SLEDAI-2K) score, excluding complement and anti-dsDNA components
- Change from Baseline in EuroQol 5-Dimension 5-Level (EQ-5D-5L)

#### 2.2.3. Exploratory Endpoints

The exploratory endpoints for patients treated with zetomipzomib compared with placebo include the following:

- Proportion of patients achieving PRR with successful taper of prednisone or equivalent to ≤5 mg by Week 17
- Proportion of patients achieving PRR with no use of prednisone or equivalent during the 8 weeks prior to the renal response assessment
- Proportion of patients who develop doubling of Baseline serum creatinine, kidney failure (receiving dialysis or kidney transplantation), or death
- Change from Baseline in antibodies (anti-dsDNA antibody, C1q autoantibody) and time to antibodies normalization or negative status (anti-dsDNA antibody normalization, anti-C1q antibody negative status)
- Change from Baseline in complement (C3, C4) and time to complement (C3, C4) normalization status
- Change from Baseline in 24-hour urine protein
- Change from Baseline in serum albumin
- Change from Baseline in serum creatinine
- Change from Baseline in eGFR

- Change from Baseline in serum lipids (serum low-density lipoprotein [LDL] cholesterol, serum total cholesterol, serum triglycerides)
- Change from Baseline in blood hemoglobin A1c (HbA1c)
- Change from baseline in the Glucocorticoid Toxicity Index (GTI) as measured by the Cumulative Worsening Score (GTI-CWS) and the Aggregate Improvement Score (GTI-AIS)
- Proportion of patients with Baseline SLEDAI-2K, excluding renal components, ≥6 with at least a 4-point improvement
- Change from Baseline in SLEDAI-2K
- Change from Baseline in 28-joint counts
- Change from Baseline in physician global assessment of disease activity (PGA) score
- Proportion of patients with relapse or proteinuric flare
- Time to relapse or proteinuric flare
- Proportion of patients with SLE Flare Index of severe, moderate, or mild
- Time to SLE Flare Index of severe, moderate, or mild
- Change from Baseline in renal biopsy histopathology and immunohistopathology (optional)
- Pharmacogenomics profile (ribonucleic acid [RNA] sequencing) and biomarkers, such as serum cytokine levels and circulating leukocytes to be determined in blood samples and urinary biomarkers
- Pharmacokinetics profile

#### 2.2.4. Safety Endpoint

The primary safety endpoint is the incidence and severity of AEs for each treatment group and patients treated with zetomipzomib compared with placebo.

#### 2.2.5. Treatment Failures

The following criteria define treatment failure:

- Prednisone or equivalent beyond that permitted (see Section 6.2.1.2)
- Prednisone or equivalent >10 mg/day for ≥3 consecutive days or for ≥7 days in total during the 8 weeks prior to the renal response assessment
- MMF or equivalent >2 g/day after Week 25
- Requiring rescue therapy (see Section 6.2.3 for details)
- Use of prohibited medications (see Section 6.2.4 and Section 13, Appendix 2 for details)
- Discontinuation of zetomipzomib or placebo

Whenever possible, a complete disease activity assessment (eg, SLEDAI-2K, SLE flare index, PGA) and laboratory assessments (hematology, chemistry, urinalysis, anti-dsDNA, and C3 and C4) should be performed to document flare prior to initiating treatment that results in a treatment failure designation. Treatment failure does not necessarily require discontinuation of zetomipzomib or placebo, thus please refer to Section 8.1.2 for individual patient stopping rules.

